(12) The allografts (human origin) also have a high substitution rate. It is important to have a low substitution rate to maintain the shape and volume of the jaw ridge for the long term to have a stable result.

Bioactive glass synthetic bone substitute (Bonalive®) is a material that has been shown to have a low substitution rate and antibacterial properties. It has been used successfully in the orthopaedics, craniofacial and ear nose and throat (ENT) specialities for the treatment of osteomyelitis, sinusitis and bony cyst cavities (13,14). There have also been a few maxillofacial surgery case reports (15,16) on its usage in the jaws. However, to the best of our knowledge, the applicability of this material in implant dentistry has not been reported in the literature.

Aim

To investigate the effectiveness of two low substitution rate bone substitutes, natural (Bio-Oss®) and synthetic (Bonalive®) in preserving the alveolar ridge of single-rooted teeth following extraction.

Key research questions

Is there a difference between natural (Bio-Oss®) and synthetic (Bonalive®) bone substitutes in preserving the alveolar ridge dimensions based on:

- I. Changes in the width of the alveolar ridge (expressed in millimetres) from augmentation (baseline) to 24-week follow-up (post augmentation).
- II. Changes in the height of the alveolar ridge (expressed in millimetres) from augmentation (baseline) to 24-week follow-up (post augmentation).
Both changes will be assessed using intra-oral scanners (this does not involve radiographs) or impressions with clinical photographs.
- III. Changes in the vertical crestal bone level assessed in millimetres, using the periapical radiographs taken pre-extraction and at 24-week follow-up and intra-oral scanners (this does not involve radiographs) or impressions with clinical photographs
- IV. Presence of bone around the alveolar ridge assessed using biopsy (up to 3mm diameter by 8mm length) of the centre of the augmented socket. The biopsy sample will be used for histology (qualitative assessment of bone infiltration) and PCR to determine the concentration (in nanograms) of gene expression for bone markers (including osteopontin, osteocalcin) at 24-week follow-up (post augmentation).

Trial design

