It is a pilot single-blind two-arm parallel randomised control trial that aims to assess the differences between two bone substitutes, natural versus synthetic. The study will mimic the routine practice, and patients will be randomly allocated to receive either the natural (control) or synthetic (intervention) bone substitutes. The patient follow-up period will be 24 weeks from the baseline data collection point.

Methods

Study setting

The study will be conducted in dental clinics in the Midlands, Southeast England and Northwest England.

Eligibility criteria for participants

Inclusion criteria

Adult patients (age >18) in need of extraction of a single-rooted tooth attending the clinics selected for the study

Single units in a dentate patient

Non-surgical extraction – no flap raised, and no bone removed

Intact socket walls post-extraction

Bleeding sockets

Stable periodontal health

ASA Class I or II patients. The American Society of Anaesthesiologists (ASA) classification is a system of physical status evaluation developed to offer clinicians a simple categorisation of a patient's physiological status to help predict operative risks (Appendix 1).

Exclusion Criteria

Multiple adjacent extractions

Presence of active periodontal disease

Socket walls not intact - >50% bone loss in any of the four walls

Sclerotic sockets post-extraction – the socket does not fill up with blood post-extraction

Denture wearer – the extraction socket site under the load of a denture

Patients on medication that can affect bone healing e.g., bisphosphonates (oral or intravenous), selective serotonin reuptake inhibitors (SSRI), methotrexate, proton pump inhibitors (PPI)

Uncontrolled diabetes

Smokers

Immunosuppressed Patients

Patients with a history of myocardial Infarction in the last year

ASA Class > II patients (17)(Appendix 1)

Intervention

The test bone substitute is Bonalive[®], bioactive glass S53P4, which contains SiO₂, Na₂O, CaO, and P₂O₅ (granule size 0.5-0.8mm) (18) Bonalive[®] is osteoconductive, meaning that it has the ability of promoting bone growth across the granules and the grafting area and slowly replace it with new bone over time. Bonalive[®] is osteostimulative and has antibacterial properties (19).

Comparator

The comparator is Bio-Oss[®], deproteinized bovine bone granules (granule size 0.25- 1mm) (20). Bio-Oss[®] is osteoconductive, which means it acts as a scaffold only for new bone to grow (21,22).

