Both products have a low substitution rate and are expected to have similar ridge support and shape maintenance capability.

Management of the bone substitutes

The bone substitutes will be used according to the manufacturers' instructions and protocols (Appendix 2 and 3). The materials are supplied in sealed sterile packaging with clearly displayed expiry dates, LOT numbers and CE marks. The materials' LOT numbers and expiry dates will be recorded on the patient records and on a separate 'Surgery Logbook' with an identification number for the patient traceable to the appropriate batch of materials.

The use of the material will follow standard surgical protocols and excess material will be discarded according to clinical waste guidelines.

Clinical procedure

The bone substitute will be used according to the ridge preservation protocol, which will be standardised between the different centres. As part of standard clinical practice, a periapical radiograph will be taken before an extraction. Following the removal of a tooth, the inflamed area of the socket will be curetted to ensure a 'clean' socket. The case will be excluded if:

- The socket walls are very sclerotic with a lack of fresh bleeding, which is essential for healing.
- The socket walls are damaged. The limit is a loss of 50% or more of one of the walls. The assessment of the extraction socket will be done by the clinicians performing the procedures (23).

The bone substitute will then be introduced using a standard sterile protocol, with gentle packing of the material in the sockets to ensure the material reaches the apex of the socket but is not condensed with pressure. The socket will then be sealed with a collagen matrix with non-resorbable sutures. Review appointment for suture removal will be required 2 weeks post-procedure.

Patients will be advised not to fly for two weeks post-procedure or until after the clinicians have reviewed them. Intra-oral scans or impressions with clinical photographs will also be taken on the day the procedure is carried out. The follow-up will take place 24 weeks post-procedure, when a PA radiograph, intra-oral scans or impressions, clinical photographs and a minimally invasive trephine biopsy will be carried out.

Management of tissue samples in the dental clinic

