The primary outcome is the difference between the two low substitution rate bone substitutes, natural (Bio-Oss[®]) and synthetic (Bonalive[®]), in preserving the alveolar ridge dimensions assessed by changes in the width (expressed in millimetres) from augmentation (baseline) to 24-week post augmentation. Assessment will be done using intra-oral scanners (this does not involve radiographs) or impressions and clinical photographs.

Secondary outcomes

- Changes in height (expressed in millimetres) from augmentation (baseline) to 24-week post augmentation. Assessment will be done using the periapical radiographs taken pre-extraction and at 24-week follow-up and intra-oral scanners (this does not involve radiographs) or impressions and clinical photographs.
- Changes in the vertical crestal bone level (expressed in millimetres) assessed with periapical radiographs taken pre-extraction and 24-week post augmentation. The technique used for this assessment will be the same as that used by Solakoglu et al.(26) to evaluate changes in the alveolar bone crest in similar research.
- Presence of bone around the alveolar ridge assessed using a biopsy, histology (qualitative assessment of bone infiltration) and PCR to determine the concentration (in nanograms) of gene expression for bone markers (including osteopontin, osteocalcin) at 24-week post augmentation.

Sample size

According to Charles et al. (27) four factors are required to calculate the sample size: significance level, power, difference between groups and standard deviation. However, considering the limited availability of information in this area (only one study was identified conducted by Rignon-Bret et al.(28)

The research team, supported by the advice provided by statisticians, decided to conduct a pilot study. Even though a pilot study does not require sample size calculation using the aforementioned four factors, (29) 15 to 20 participants per group are required to ensure the scientific validity of the pilot study results (30). More recently, further information has been provided for the validity of the results of pilot RCT indicating a wider range of participants (31). Therefore, we used a pragmatic approach informed by the literature and we will recruit a total of 34 participants with 17 per group. The results of the pilot study will generate the four factors to calculate the sample size for the full-scale RCT.

Recruitment

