Recruitment will be focused on private dental clinics in the Midlands, Southeast England and Northwest England

Clinicians: Experienced Implant surgeons at centres approved by lead researchers. Approval will be based on appropriate clinical setup, clinician experience and patient volume.

Patients: Patients who meet the inclusion criteria will be invited to take part in the study. They will consent to using either of the bone substitute materials and be randomly allocated to a group.

Recruitment will start as soon as ethics approval has been granted.

The recruitment strategy will increase potential participants' awareness of the health problem being studied and its potential impact on their health.

Clinician-patient ratio

The patients will be spread across 2-4 surgeries to ensure we meet the target sample size in a few months.

Randomisation, sequence generation, allocation and blinding

The randomisation, sequence generation and allocation concealment will be performed using the sealed envelope online system (<https://www.sealedenvelope.com/>) (32) . The randomisation will be 1:1. The patient will be the unit of randomisation and intervention.

All patients receiving the bone substitutes will be blinded to the treatment in our study. However, patients will know which bone substitute they have received after their final review at 24-week follow-up.

Data collection

Clinicians will collect data at baseline and at 24-week follow-up using a paper template. Then data will be transferred into Excel and SPSS and prepared for the data analysis. All paper records, except consent forms, will be destroyed at patients' last visit. Secure and irreversible destruction processes will include shredding and disposal of records using the University's confidential waste service.

Data management

The procedure will be conducted using the data management template provided by UKRI. Data will be managed following the procedure used in previous studies (26,28). Input data will

be saved and stored on a password-protected system. Only individuals authorised by the CI will be allowed to access the data. Paper data, such as Patients' informed consent will be kept in a locked cabinet by the clinicians.

Statistical methods

The primary analysis will be the intention-to-treat (ITT), including all randomised participants in the assigned group, regardless of their adherence to the protocol or their withdrawal.

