The risk of allergy, infection and lack of bone integration will be monitored by the clinicians during the study keeping in contact with their patients.

Harm

We do not envisage any specific harm from these products, which are approved and in clinical use already, other than risks of potential complications from surgical procedure. This will be minimised through careful and appropriate case selection (healthy ASA Class I and II), surgical procedures with standard precautions for infection control and pre- and post-operative care. Additionally, the principal investigator enquired the Medical and Healthcare Products Regulatory Agency (MHRA) regarding the use of these bone substitutes in the study. The MHRA replied that “as you are using the medical devices on human subjects *within* its CE marked intended use, as per the manufacturers IFU and the intention of the study is not to generate data to change or extend the indications of the CE marked device, you do not need to notify MHRA of this study” (Appendix 8).

Auditing

No audit has been planned at this time.

Research ethics approval

Ethics approval will be sought from the Health Ethics Review Panel at the University of Central Lancashire (UCLan)

Protocol amendments

We are not expecting to make any changes to the eligibility criteria, outcomes or analyses during our study

Consent, invitation and confidentiality

All documentation related to information and consent for clinicians and patients has been enclosed in the protocol and approved by the UCLan ethics committees. The procedures followed for consent and confidentiality are described in the following paragraphs.

Informed consent

Clinicians participating in the study will recruit their patients and obtain consent from them.

Patients' recruitment and informed consent

After assessing patients' eligibility for the study, clinicians will provide an information letter and consent form to each patient, who will get a week to consider their participation. The clinicians will submit all signed consent forms to the PI so that they can be stored in the PI's office in a locked cabinet located within the School of Dentistry.

The baseline information will be transferred onto an Excel spreadsheet and stored electronically in a password protected UCLan computer. Anyone who is deemed unsuitable to participate will be offered a copy of their record and the electronic record will be destroyed in line with the University's confidential procedure.

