Declaration of interest

None

Dissemination policy

The dissemination of the study will begin immediately with the publication of the protocol. The results of this trial will be presented at national and international conferences. They will be submitted as scientific manuscripts to peer-reviewed journals. The trial results aim to inform patients, policymakers, and all other stakeholders that might benefit from the results.

The results of the trial will be disseminated to service users and their families via media, to healthcare professionals via professional training and meetings, and researchers via conferences and publications. The publications generated by this study may be used as training materials for dentists with an interest in implantology.

Ancillary post-trial care

We are not envisaging the need for the provision of post-trial care. Nevertheless, all participants will be provided with an emergency contact number to reach the study

investigators so that they can receive the necessary support when they have any questions or problems.

Patient and Public Involvement (PPI)

The research protocol was developed during the COVID Omicron wave, February-March 2022, thus it was impossible to reach the patients and members of the public and get their input into the protocol.

Discussion

Following the extraction of teeth their supporting alveolar bone undergoes remodelling, which can result in the loss of height and width of the bony ridge; this is most marked in the aesthetic zone (anterior aspect of the upper jaw, the maxilla) (34,35).

To minimise this loss of ridge volume, the ridge preservation technique has been developed, which involves the insertion of bone substitute material to act as a space maintainer and scaffold for new bone growth (36–38)

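### The week-24 trephine biopsy falls at the last scheduled contact, so complications arising after that visit have no scheduled ascertainment and no stated route into study data

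*Combined protocol and SAP*

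**What the plan says.** The biopsy is done at the 24-week follow-up, together with the radiograph, scans or impressions: "clinical photographs and a minimally invasive trephine biopsy will be carried out" (Clinical procedure). Key research questions describes it as a "biopsy (up to 3mm diameter by 8mm length) of the centre of the augmented socket". It supplies the histology and PCR outcomes listed under Secondary outcomes. Clinical procedure calls the pre-extraction radiograph part of standard practice; it does not say this of the biopsy.

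The same visit closes the patient's participation:

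- Trial design: "The patient follow-up period will be 24 weeks from the baseline data collection point".
- Randomisation, sequence generation, allocation and blinding: "patients will know which bone substitute they have received after their final review at 24-week follow-up".
- Table 1 has histology and bone markers only in the W24 column, labelled Close-out, with no later column. It has no adverse-event row at any visit.
- Data collection: data are gathered at baseline and at 24 weeks, and paper records other than consent forms are destroyed at the last visit.

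On safety, Harm expects nothing specific from the products "other than risks of potential complications from surgical procedure", and says that risk will be reduced by case selection, infection control and care before and after surgery. Risk and safety issues has clinicians monitor allergy, infection and failed integration during the study by staying in touch with patients. Ancillary post-trial care says "We are not envisaging the need for the provision of post-trial care", but gives every participant an emergency number for the investigators.

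After grafting there is a planned contact: "Review appointment for suture removal will be required 2 weeks post-procedure" (Clinical procedure).

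**The concern.** The protocol names surgical complications as the harm that remains, then carries out a second surgical procedure on the day planned follow-up stops. An infection, bleed or disturbance of the graft that develops after the patient goes home would reach the investigators only if the patient rang or the clinic happened to hear of it. No form, window or row in Table 1 would then carry it into the dataset.

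Two things are at stake. One is the safety of patients who undergo a procedure done to supply study outcomes. The other is the harms information passed to the full-scale trial. If that trial keeps the biopsy, its designers will want to know how well patients tolerated it, and this pilot would give them an incomplete count. No formal monitoring committee (Data monitoring) and no audit (Auditing) is planned that might pick up the gap.

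**Working it through.** **Number of patients.** Sample size: "we will recruit a total of 34 participants with 17 per group". Two groups of 17 give 17 × 2 = 34, which reproduces the stated total. It is a pragmatic size with no power calculation behind it. No dropout rate is given, so 34 is the most that can be biopsied.

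**Scheduled observation after each procedure** (next or last scheduled contact minus time of procedure):

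| Procedure | Time | Contact | Scheduled observation |
|---|---|---|---|
| Graft placement | week 0 | week 2, suture removal | 2 − 0 = 2 weeks |
| Trephine biopsy | week 24 | week 24, final review | 24 − 24 = 0 weeks |

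**What could be learned from n biopsied patients.** The documents give no complication rate, so the rates p below are assumptions for illustration. Expected cases are n × p; the chance of at least one is 1 − (1 − p)^n. With n = 34:

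| Assumed rate p | Expected cases | Chance of at least one |
|---|---|---|
| 1% | 0.34 | 0.29 |
| 2% | 0.68 | 0.50 |
| 5% | 1.7 | 0.83 |
| 10% | 3.4 | 0.97 |

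If all 34 were asked and none reported a complication, the one-sided 95% upper limit for the rate would be 1 − 0.05^(1/34) = 8.4%. If withdrawals left 30 or 27 patients (assumed), the limit would be 9.5% or 10.5%.

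**Effect of passive capture.** Let c be the fraction of post-visit complications that come to notice and are recorded. Expected recorded cases are n × p × c. With no reports from 34 patients, the 8.4% limit applies to p × c, so the limit for p itself is 8.4% divided by c. The documents give no basis for c. The present schedule therefore cannot support even the modest 8.4% statement.

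**The case against.** The best defence is that the protocol is not silent. Harm promises post-operative care. Risk and safety issues has clinicians in touch with patients they recruited from their own clinics. The emergency number reaches the investigators. Complications during the biopsy visit can be seen on the spot.

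These points stand, and they rule out stronger readings that a reader might infer:

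- *The biopsy complication rate would be zero by design, or later events would go wholly unsought and unreported.* The text does not support this. It allows passive capture, which may under-count but does not force a zero.
- *All surgical complications in all 34 patients go unobserved.* The gap covers only events after the patient leaves the visit, in however many are biopsied.
- *The sections contradict one another.* They do not; this is an omission. Monitoring during the study is not defined per patient, and the Study summary gives a 12-month study period, so some contact after week 24 may be intended.

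The comparison with the week-2 review also has limits. That visit is described as suture removal, no sutures are mentioned for the biopsy, and Table 1 collects no adverse events at week 2 either. It compares scheduled contacts, not documented safety windows.

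Finally, the Standard Operating Procedures, cited for documenting reasons for discontinuation, were not available to this review, nor were the consent pages. A post-biopsy check in either cannot be excluded.

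The core remains: none of the general promises has a schedule, a form or a link to the trial data, and the emergency number depends on the patient calling.

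**Conclusion.** The point holds as an omission in ascertainment. Scheduled observation after the biopsy is 0 weeks for up to 34 patients, and the documents state no route by which a later complication enters the study data. Passive capture may under-count such events. By how much cannot be estimated, because the documents give neither a complication rate nor any basis for the fraction captured.

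This rests on reading the 24-week visit as the patient's last scheduled contact, which Trial design, Table 1 and the description of it as the final review all support, and on there being no post-biopsy check in material not supplied.

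The primary outcome and its analysis are unaffected, and biopsy tolerability is not a stated objective. The change is still worth making before recruitment, because it improves patient safety and the harms data at little cost.

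**What to change.** Reconcile the end of participation (Trial design, Table 1, the final-review wording and Ancillary post-trial care) with the monitoring statement under Risk and safety issues:

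1. Define an adverse-event record, since the plan has none to extend, and state that it covers a period after the biopsy.
2. Complete it through one telephone contact per patient by the treating clinic, at an interval the investigators set and justify. Strategies for monitoring and improving protocol adherence already lists telephone calls, but as an optional adherence measure, so this use must be stated.
3. Record biopsy events separately from graft events.
4. Add the contact and an adverse-event row to Table 1.
5. Move the destruction of paper records and the disclosure of allocation until after that contact, so that records still exist and reports come from patients who are still blinded.

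If the Standard Operating Procedures already contain such a check, a cross-reference and item 5 may be enough.

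Cost: up to 34 calls, a short form, the Table 1 additions and wording changes. Participation ends slightly later and patients learn their allocation slightly later. No extra visit, procedure or staff is needed, and no clinical management rule is proposed.

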The procedure for processing the sample in the laboratory will be similar to that used in a study by Li et al. (25) Frozen tissue samples will be thawed in RNAlater®-ICE and lysed for RNA extraction using Qiagen RNeasy kit following the manufacturer's instructions. Following treatment with DNase-1 reagent and reverse-transcription of RNA samples using the SuperScript® VILOTM cDNA synthesis. SYBR green-based qPCR assays will be performed to analyse osteogenic gene expression, including Runx2, alkaline phosphatase, osteopontin and osteocalcin. The relative transcript levels of genes of interest will be analysed using the comparative CT (ΔΔCT) method. The range of relative transcript levels of the genes of interest will be presented as bar graphs, and statistical analysis will be performed at the level of ΔΔCT.

Table 1 Schedule of enrolment, intervention and assessments

	Study period				
	Enrolment	Allocation	Post-allocation		Close-out
Timepoint (weeks)	-W0	W0	W0	W2	W24
Enrolment					
Eligibility screen for patients	x				
Informed consent from patients	x				
List of other procedures	x				
Randomisation of patients		x			
Interventions					
Synthetic bone			x		
Natural bone			x		
Suture removal				x	
Assessments (Outcomes)					
Width			x		x
Height			x		x
Crestal bone					x
Histology					x
Bone Markers					x

Figure 1 CONSORT study flowchart

Criteria for discontinuing or modifying allocated interventions

- Participant withdraws consent
- The trial is discontinued
- Participant has an adverse reaction

The reasons for discontinuation will be documented (see Standard Operating Procedures).

Strategies for monitoring and improving protocol adherence

There are some measures that clinicians could adopt to improve patients' adherence to the research protocol, such as telephone calls, text reminders, and social support to educate patients. In addition, clinicians will have to create a welcoming, non-judgmental and accepting environment; educate patients about their role as research participants; establish a routine while maintaining flexibility; provide incentives for participation, parking spaces, and videoconferences.

Outcomes

Primary outcome

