Missing data will be assessed and treated using multiple imputations if missing at random (MAR).

To check for normality, each variable will be analysed using the Shapiro-Wilk test.

Primary outcome

The primary outcome is the difference between the two bone substitutes, natural (Bio-Oss[®]) and synthetic (Bonalive[®]), in preserving the alveolar ridge dimensions assessed by changes in the width of the alveolar ridge (expressed in millimetres) from augmentation (baseline) to 24-week post augmentation. It is expected to be a continuous variable, therefore, the comparison between groups at 24 weeks will be performed using a linear regression model (ANCOVA), including the baseline measurements as the covariates. The recent literature suggests using of ANCOVA as the statistical method of choice for the analysis of intervention effect and adjustment for baseline variables for three reasons: efficiency, precision and power (33).

Secondary outcomes

- The changes in the height of the alveolar ridge (expressed in millimetres) from grafting (baseline) to 24-week follow-up (post grafting) assessed using either intra-oral scanners or impressions and clinical photographs. It is expected to be a continuous variable; therefore, the comparison between groups at week 24 will be performed using the unpaired t-test for a normally distributed variable or the Mann-Whitney U test for non-normally distributed.
- The changes in vertical crestal bone levels between the groups (expressed in millimetres) will be compared using an unpaired t-test or Mann-Whitney U test according to the variable distribution. This will be assessed using radiographs pre-extraction and at 24-week follow-up.
- Presence of bone will be assessed using biopsy used for histology (qualitative assessment of bone infiltration) and PCR to determine the concentration (in nanograms) of gene expression of the bone markers (including osteopontin and osteocalcin).

- The comparison of the concentration of gene expression between the groups at 24-week will be performed using the unpaired t-test for a normally distributed variable or the Mann-Whitney U test for non-normally distributed

Data monitoring

This trial is designed to minimise the risk, as demonstrated in the previous trials by Rignon-Bret et al. (28) and Solakoglu et al. (26). Therefore, no formal committee has been organised, and no interim analysis of the impact of the intervention has been planned.

Risk and safety issues

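### PCR is named as a measure of presence of bone around the ridge, but the described assay supports only a between-arm contrast in relative marker expression in a central socket core

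*Combined protocol and SAP*

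**What the plan says.** Four places put PCR under a presence-of-bone outcome: the Study summary (research question iv), Key research questions (item IV), Outcomes (Secondary outcomes) and Statistical methods (Secondary outcomes). The Outcomes section has "Presence of bone around the alveolar ridge assessed using a biopsy, histology (qualitative assessment of bone infiltration) and PCR to determine the concentration", and the Statistical methods section has "Presence of bone will be assessed using biopsy used for histology (qualitative assessment of bone infiltration) and PCR". The first three add that the bone is around the alveolar ridge; the Statistical methods section does not. The PCR quantity is given as "concentration (in nanograms) of gene expression for bone markers (including osteopontin, osteocalcin) at 24-week post augmentation".

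Other parts of the plan describe the measurement differently:

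- **Laboratory processing of tissue samples for PCR.** The assay covers "osteogenic gene expression, including Runx2, alkaline phosphatase, osteopontin and osteocalcin". "The relative transcript levels of genes of interest will be analysed using the comparative CT" method, and "statistical analysis will be performed at the level of" ΔΔCT.
- **Key research questions, item IV.** The biopsy is "of the centre of the augmented socket", up to 3 mm by 8 mm.
- **Management of tissue samples in the dental clinic.** Each core is split into one segment for histology and one for PCR.
- **Abstract (Methods) and Table 1.** Bone markers and histological bone infiltration are separate items.
- **Statistical methods.** Gene expression gets a between-group test (unpaired t-test or Mann-Whitney U). Histology is qualitative and gets none.

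**The concern.** The outcome names one construct, presence of bone, and gives it two measures. Only one of them, PCR, is numerical and formally tested. Key research question IV also sits under a stem that asks about preserving ridge dimensions. A significant PCR result would therefore be filed under a label about bone, within a question about the ridge, although the assay measures neither.

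Two features of the described measurement cause this. A comparative CT result is normalised to a reference gene in the same sample and expressed relative to a calibrator, so it carries no absolute quantity. The core also comes from the socket centre, so it gives no direct information on bone elsewhere around the ridge.

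The pilot is meant to inform a full-scale trial, so a mislabelled outcome could be carried forward. The issue is separate from the unit problem (nanograms against ΔΔCT): correcting the unit alone would leave PCR labelled as presence of bone.

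**Working it through.** The plan gives no numerical figure for this outcome that could be reproduced. Its one design figure is consistent (2 × 17 = 34), and the point does not depend on it. The check is the algebra of the assay that the plan names. All copy numbers below are assumptions for illustration.

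**Formulas.** ΔΔCT = (CT_target − CT_ref) in the sample − (CT_target − CT_ref) in the calibrator. Fold = 2^(−ΔΔCT). One CT unit is a two-fold difference.

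**Step 1: does the amount of tissue show?** Assume 2,000 target and 10,000 reference copies per unit of tissue, a calibrator with 1,000 target and 10,000 reference copies, and CT = log2(10^10 / copies). The calibrator term is log2(10) = 3.32.

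| Tissue amount | CT target | CT reference | ΔΔCT | Fold |
|---|---|---|---|---|
| 1 | 22.25 | 19.93 | -1.0 | 2.0 |
| 0.5 | 23.25 | 20.93 | -1.0 | 2.0 |
| 0.1 | 25.58 | 23.25 | -1.0 | 2.0 |
| 0.01 | 28.90 | 26.58 | -1.0 | 2.0 |

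Raw CT moves, but the analysed quantity does not. A 100-fold difference in tissue yielding RNA is invisible on the ΔΔCT scale.

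**Step 2: does any value mean present?** Keep the sample fixed and change only the target copies in the calibrator (reference 10,000).

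| Calibrator target copies | ΔΔCT | Fold |
|---|---|---|
| 500 | -2.0 | 4.0 |
| 1,000 | -1.0 | 2.0 |
| 4,000 | +1.0 | 0.5 |

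The same sample reads as 4.0, 2.0 or 0.5. The plan names no calibrator, reference gene or cut-off. It says the procedure will resemble that of a cited scaffold study, which may supply the first two. A rule for calling bone present would still be missing from this plan.

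**Step 3: what survives?** A calibrator common to both arms drops out of the between-arm difference in mean ΔΔCT. The contrast in relative expression is therefore valid.

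**Step 4: can that contrast be read as bone?** If reference-gene expression per cell is stable, the signal is roughly (share of bone-forming cells) × (expression per cell). As an illustration only:

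- Share ×2 and activity ×0.5: log2(2 × 0.5) = log2(1) = 0, so there is no CT difference although the share doubled.
- Share ×1 and activity ×0.5: log2(0.5) = -1, a 1 CT difference at equal share.

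The documents give no activity ratio. The Intervention and Comparator sections do describe the test material as stimulating bone and the comparator as a scaffold only. A difference in activity between arms is thus conceivable on the plan's own account, but that is an inference.

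**Step 5: site.** A full core is π × 1.5² × 8 ≈ 56.5 mm³. If it is split equally (an assumption), the PCR segment is about 28.3 mm³, all from the socket centre.

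**The case against.** The strongest reply is that this is a loose umbrella label and nothing more. The outcome sentence gives each assay its own task: histology for bone infiltration, PCR for marker expression. The Abstract and Table 1 already keep the two apart, and the test in the Statistical methods compares gene expression, not bone. No sentence says that higher expression means more bone. Much of this stands. It limits the point to the outcome definitions and supplies the wording for the fix. It does not remove the point, because the sections that define and analyse the outcome still present both assays as assessing presence of bone.

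A reader might infer several stronger faults that the documents do not support:

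- **The single 24-week sample, without baseline or ungrafted tissue, is a flaw.** The outcome is defined at 24 weeks and the arms are randomised, so a comparison at that time needs no baseline. Histology has the same timing.
- **The PCR comparison is invalid.** It is valid as a contrast in relative expression.
- **Outcome IV cannot show bone at all.** Histology of the other segment can show bone in the core qualitatively.
- **PCR carries no information on tissue composition.** It carries some, confounded with activity per cell.
- **The two-fold figures measure a likely error.** They were chosen to show the mechanism. Four genes are assayed, and nothing says that they would all offset together.

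The site wording applies to histology as much as to PCR. It is a reason to correct the outcome label, not evidence against the assay.

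**Conclusion.** The concern holds for the PCR component of one secondary outcome. As described, PCR supports a between-arm contrast in relative osteogenic marker expression in a core from the socket centre at 24 weeks. It does not support a statement on presence or amount of bone, nor one on bone around the ridge. The definitions also conflict with the Abstract and Table 1, which separate markers from histology.

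The conclusion rests on the comparative CT method being applied as the laboratory section states, and on no rule for presence existing elsewhere in the plan. It does not depend on the assumed copy numbers, because the cancellation of tissue amount follows from the formula.

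The consequence is one of interpretation. The only formal test under this outcome would carry a label that it cannot support. The primary width outcome, its ANCOVA and the sample size of 34 are unaffected. The correction is worth making before analysis, but it is not critical to the trial.

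**What to change.** In the Study summary, Key research questions IV, Outcomes and Statistical methods, split the outcome to match the Abstract and Table 1:

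- (a) Qualitative bone infiltration in the centre of the augmented socket at 24 weeks, by histology.
- (b) Relative expression of the osteogenic markers in the same core at 24 weeks, by PCR, compared between arms on the ΔΔCT scale. State that a higher or lower level will not be reported as more or less bone.

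In the Study summary, Key research questions IV and Outcomes, replace the phrase about bone around the alveolar ridge with the centre of the augmented socket. The Statistical methods section does not use that phrase. Item (b) also replaces the nanogram unit with the scale that the laboratory section uses.

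The cost is wording in four places and a narrower claim from PCR. No sample, assay or sample-size figure changes. Calling item (b) exploratory, or showing it beside each patient's histology, is optional.
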